13.1.9.2. Safety Analysis

13.1.9.2.1. Phase 1 Safety Analysis

All safety analyses will be performed on the safety analysis set in Phase 1. Adverse event listings and tabulated summaries of TEAEs will be generated for each dose level, and for all Phase 1 patients. Treatment-emergent AEs are AEs that occur after administration of the first dose of study drug and through 30 days after the last dose of study drug. Additionally, AESIs, SAEs, the number of patients enrolled, the number of patients evaluable for dose escalation, number of patients with DLTs, and TP-0184 dose interruption and reduction due to TEAEs will be described for each dose level and for all Phase 1 patients.

Descriptive statistics for the actual values and changes from baseline of vital signs, weight, ECOG scores will be tabulated by scheduled time point by each dose level, and for all Phase 1 patients. ECHO or MUGA scans, cardiac markers, and other test results will be analyzed using proper statistical methods for each dose level, and for all Phase 1 patients.

13.1.9.2.2. Phase 2 Safety Analysis

Safety will be evaluated by the incidence of AEs, severity and type of AEs, SAEs, and by changes from baseline in the patient's vital signs, weight, and clinical laboratory results using the safety population. Exposure to study drug and reasons for discontinuation will be tabulated.

Treatment-emergent AEs will be tabulated according to the Medical Dictionary for Regulatory Activities (MedDRA) and will include the following categories:

- TEAEs
- Drug-related TEAEs
- Grade 3 or higher TEAEs
- Grade 3 or higher drug-related TEAEs
- The most commonly reported TEAEs (i.e., those events reported by $\geq 10\%$ of patients in any treatment group)
- SAEs
- AESI

A listing of TEAEs resulting in study drug discontinuation will be provided.

Descriptive statistics for the actual values of clinical laboratory parameters (and/or change from baseline in clinical laboratory parameters) will be presented for all scheduled measurements over time. Mean laboratory values over time will be plotted for key laboratory parameters.

Descriptive statistics for the actual values and changes from baseline of vital signs, weight, ECOG scores will be tabulated by scheduled time point.

Shift tables for laboratory parameters will be generated based on changes in NCI CTCAE v.5 grade from baseline to the worst post baseline value. Graphical displays of key safety parameters, such as scatter plots of baseline versus worst post baseline values, may be used to understand the TP-0184 safety profile.

All concomitant medications collected from screening through the study period will be classified to preferred terms according to the World Health Organization (WHO) Drug Dictionary.

Additional safety analyses may be performed to most clearly enumerate rates of toxicities and to further define the safety profile of TP-0184.

13.1.9.3. Pharmacokinetics and Biomarkers

Pharmacokinetic parameters including C_{max} , C_{trough} , t_{max} , and AUC_{τ} , will be estimated using standard noncompartmental methods. Other parameters may also be computed. Actual sample collection times will be used rather than scheduled (nominal) collection times, where available ([Table 7](#) and [Table 8](#)). Data obtained from the current study may be modeled, either singularly or in conjunction with data from other studies (for example, for population PK analyses).

Exploratory endpoints including biomarker analysis will be summarized using mean, standard deviation, median, and minimum/maximum levels of continuous, and frequencies and percentages of categorical biomarker measures for the potential biomarker parameters ([Section 11.2](#)). The correlations of biomarker results with pharmacokinetic parameters and measures of efficacy may be explored, if deemed appropriate.

13.1.9.4. Patient-reported Outcomes

Patient-reported outcome assessments using BFI will be analyzed to determine any measurable changes in the severity of fatigue based on the worst fatigue score experienced during the past 24-hours. The analysis will be performed using proper statistical methods for collected scores using SAS in Phase 2. Missing items in BFI scores will be handled based on each individual assessment and according to the developer's guidelines. Investigation of missing patterns and details of imputation will be discussed in the SAP. Similar analyses will be performed using BFI assessments in Phase 1 if data is applicable.

14. DIRECT ACCESS TO SOURCE DATA/DOCUMENTS

14.1. Study Monitoring

Before an investigational site can enter a patient into the study, a monitor from SDP Oncology or a representative will visit the investigational study site to:

- Determine the adequacy of the facilities
- Discuss with the investigator(s) and other personnel their responsibilities with regard to protocol adherence, and the responsibilities of SDP Oncology or its representatives. This will be documented in a Clinical Study Agreement between SDP Oncology and the investigator.

During the study, a monitor from SDP Oncology or representative will have regular contacts with the investigational site, for the following:

- Provide information and support to the investigator(s)
- Confirm that facilities remain acceptable
- Confirm that the investigational team is adhering to the protocol, that data are being accurately recorded in the case report forms, and that investigational product accountability checks are being performed
- Perform source data verification. This includes a comparison of the data in the case report forms with the patient's medical records at the hospital or practice, and other records relevant to the study. This will require direct access to all original records for each patient (eg, clinic charts).
- Record and report any protocol deviations not previously sent to SDP Oncology.
- Confirm AEs and SAEs have been properly documented on eCRFs and confirm any SAEs have been forwarded to SDP Oncology and those SAEs that met criteria for reporting have been forwarded to the IRB.
- The monitor will be available between visits if the investigator(s) or other staff needs information or advice.

During the COVID-19 public health emergency, traditional on-site monitoring might be difficult for reasons such as: (1) sites may not be able to accommodate monitoring visits (eg, due to staffing limitations or site closures) or (2) monitors may not be able to travel to trial sites. When planned on-site monitoring visits are not possible, the reason should be documented and available for review by SDP Oncology and during FDA inspections. On-site monitoring visits may be replaced with remote monitoring visits during the COVID-19 public health emergency (Food and Drug Administration, January 2021).

14.2. Audits and Inspections

Authorized representatives of SDP Oncology, a regulatory authority, an Independent Ethics Committee, or an Institutional Review Board may visit the site to perform audits or inspections, including source data verification. The purpose of an SDP Oncology audit or inspection is to systematically and independently examine all study-related activities and documents to

determine whether these activities were conducted, and data were recorded, analyzed, and accurately reported according to the protocol, Good Clinical Practice guidelines of the International Conference on Harmonization, and any applicable regulatory requirements. The investigator should contact SDP Oncology immediately if contacted by a regulatory agency about an inspection.

14.3. Institutional Review Board/Independent Ethics Committee

The investigator must obtain IRB or IEC approval for the study. Initial IRB/IEC approval of the protocol and all materials approved by the IRB/IEC for this study, including the patient ICF and any recruitment materials must be maintained by the study site/investigator and made available for inspection by the study monitor or any regulatory authorities with an interest in this study.

15. QUALITY CONTROL AND QUALITY ASSURANCE

To ensure compliance with Good Clinical Practices and all applicable regulatory requirements, SDP Oncology may conduct a quality assurance audit. Refer to [Section 14.2](#) for more details regarding the audit process.

16. ETHICS

16.1. Ethics Review

The Principal Investigator must obtain IRB approval for the investigation. Initial IRB approval, and all materials approved by the IRB for this study including the patient consent form and recruitment materials must be maintained by the Investigator and made available for inspection.

The final study protocol, including the final version of the Informed Consent Form, must be approved or given a favorable opinion in writing by an IRB or IEC as appropriate. The investigator must submit written approval to SDP Oncology before he or she can enroll any patient/subject into the study.

The Principal Investigator is responsible for informing the IRB or IEC of any amendment to the protocol in accordance with local requirements. In addition, the IRB or IEC must approve all advertising used to recruit patients for the study. The protocol must be re-approved by the IRB or IEC upon receipt of amendments and annually, as local regulations require.

The Principal Investigator is also responsible for providing the IRB with reports of any reportable serious adverse drug reactions from any other study conducted with the investigational product. SDP Oncology will provide this information to the Principal Investigator.

Progress reports and notifications of serious adverse drug reactions will be provided to the IRB or IEC according to local regulations and guidelines.

16.2. Ethical Conduct of the Study

The study will be performed in accordance with ethical principles that have their origin in the Declaration of Helsinki and are consistent with ICH Good Clinical Practice, applicable regulatory requirements and the SDP Oncology's policy on Bioethics.

16.3. Informed Consent

The Principal Investigator(s) at each site will ensure that the patient is given full and adequate oral and written information about the nature, purpose, possible risk and benefit of the study. Patients must also be notified that they are free to discontinue from the study at any time. The patient should be given the opportunity to ask questions and allowed time to consider the information provided.

The patient's signed and dated informed consent must be obtained before conducting any study procedures. If an informed consent cannot be obtained and documented from a prospective trial participant (or legally authorized representative) as signed paper copy, the consent form may be provided electronically by the Investigator/designee.

Where a prospective trial participant (or legally authorized representative) is unable to print the informed consent document provided electronically by the Investigator/designee, an electronic signature process is not available, and the prospective trial participant must meet time-sensitive eligibility criteria, the investigator may consider using the alternative process to satisfy FDA requirements for obtaining and documenting informed consent and IRB approved process. ([Food and Drug Administration, January 2021](#))

The Principal Investigator(s) must maintain the original, signed Informed Consent Form. A copy of the signed Informed Consent Form must be given to the patient.

17. DATA HANDLING AND RECORDKEEPING

17.1. Data Protection

Monitors, auditors, and other authorized agents of the Sponsor and/or its designee, the IEC(s)/IRB(s) approving this research, and the FDA, as well as that of any other applicable regulatory agency(ies), will be granted direct access to the study patient's original medical records for verification of clinical study procedures and/or data, without violating the confidentiality of the patient to the extent permitted by laws and regulations. In any presentation of the results of this study or in publications, the patient's identity will remain confidential.

All personal data collected and processed for the purposes of this study should be managed by the investigator and his/her staff with adequate precautions to ensure the confidentiality of those data, and in accordance with the Health Insurance Portability and Accountability Act and applicable national and/or local laws and regulations regarding personal data protection.

17.2. Inspection of Records

SDP Oncology will be allowed to conduct site visits to the investigation facilities for the purpose of monitoring any aspect of the study. The Investigator agrees to allow the monitor to inspect the drug storage area, study drug stocks, drug accountability records, subject charts and study source documents, and other records relative to study conduct. If on-site monitoring visits are not possible SDP Oncology will be allowed to do remote monitoring to maintain oversight of the clinical site.

17.3. Retention of Records

The Principal Investigator must maintain all documentation relating to the study for a period of 2 years after the last marketing application approval, or if not approved 2 years following the discontinuance of the test article for investigation. If it becomes necessary for SDP Oncology or the Regulatory Authority to review any documentation relating to the study, the Investigator must permit access to such records.

18. PUBLICATION POLICY

The publication policy for the study will be described in the clinical study agreement. To avoid disclosures that could jeopardize proprietary rights, the investigator agrees to give SDP Oncology the right to review all manuscripts, abstracts, and presentations related to this study prior to their submission for publication or presentation. SDP Oncology may use these data now and in the future for presentation or publication at SDP Oncology's discretion or for submission to government regulatory agencies.

Authorship among Investigators generally will be based on the extent of significant contribution, including scientific and clinical, to the publication.

20. APPENDICES

**APPENDIX 1. CONSIDERATION OF RESPONSE FOR COMPOSITE
ENDPOINT**

Patient population	Hemoglobin increase ≥ 1.5 in the absence of transfusion / 8 weeks	RBC transfusion free / 8 weeks	Reduction in units of ≥ 4 RBC transfusions / 8 weeks
High transfusion burden (≥ 4 U transfusion)	X	X	X
Low transfusion burden (1-3 U transfusion)	X	X	

APPENDIX 2. BLRM STATISTICAL METHODS

17.2.1 Introduction

In the Dose Escalation part of the study, an adaptive Bayesian logistic regression model (BLRM) with EWOC will be used to guide dose escalation and estimate the MTD(s) based on occurrence of DLT during Cycle 1. This appendix provides details on the statistical model, prior definition and operating characteristics in order to illustrate the performance of the design in estimating the MTD under various dose-toxicity relationships through simulations. Finally, hypothetical dose escalations scenarios will be presented to illustrate the dose allocation in first cohorts of the study.

20.1.1. Dose Escalation Method

17.2.2.1 Statistical Model

The DLT-dose relationship in the Dose Escalation part of the study is described by a 2-parameter logistic model:

$$\text{logit}(\pi_{(d)}) = \log(\alpha) + \beta \log(d/d^*), \alpha > 0, \beta > 0$$

where

$\text{logit}(\pi_{(d)}) = \log \left(\frac{\pi_{(d)}}{1-\pi_{(d)}} \right)$ and $\pi_{(d)}$ is the probability of a DLT at dose d . Doses are rescaled as d/d^* with reference dose $d^* = 90 \text{ mg}$ of TP-0184. As a consequence, α is equal to the odds of toxicity at d^* . Note that for a dose equal to zero, the probability of toxicity is zero.

The MTD is the highest drug dosage that is unlikely (< 25% posterior probability) to cause DLT in more than 33% of the treated patients in the first cycle of TP-0184 treatment.

20.1.1.1. Planned Dose Escalation Levels

This study currently plans and expects to complete dose escalation with the following provisional dose levels:

Table 10 Planned Dose Escalation Levels

Dose Level	Dose (Daily Schedule)
-1	10 mg
1	20 mg
2	40 mg
3	60 mg
4	90 mg
5	120 mg
6	160 mg
7	210 mg
8	270 mg

Note: An intermediate dose level between the planned dose levels may be explored. In addition, based on safety during the escalation phase, additional dose schedules than those outlined in the

table may be explored after discussion and concurrence with SRC members and SDP Oncology clinical team.

Intra-patient dose escalation is not permitted in the protocol.

20.1.1.2. Prior Specifications

The bivariate normal prior for the BLRM parameters with a reference dose level of 90 mg is obtained as follows:

The following noninformative prior for $(\log(\alpha), \log(\beta))$ was used:

- The mean of $\log(\alpha)$ was set to -0.847 and mean of $\log(\beta)$ was set to 0.913 to allow the median DLT rate to be around 1%.
- The standard deviation of $\log(\alpha)$ was set to 1.275, and the standard deviation of $\log(\beta)$ to 0.482, which allows for considerable prior uncertainty for the dose-toxicity profile.
- The correlation between $\log(\alpha)$ and $\log(\beta)$ was set to -0.9.

Table 11 Prior Parameters for Bivariate Normal Distribution of Model Parameters

Parameters	Means	Standard Deviations	Correlation
$\log(\alpha), \log(\beta)$	(-0.847, 0.913)	(1.275, 0.482)	-0.9

Table 12 Prior Distribution Summaries Derived from Priors in Table 11

TP-0184 Dose (mg)	Prior Probabilities Pr(DLT) is in Interval:			Mean	SD	Quantiles		
	(0, 0.16]	(0.16, 0.33]	(0.33, 1]			2.5%	50%	97.5%
20	0.8685	0.0744	0.0571	0.06784	0.13677	0	0.0101	0.5253
40	0.7191	0.1414	0.1395	0.13674	0.18611	0.00026	0.05436	0.6946
60	0.5463	0.2089	0.2448	0.21414	0.21583	0.00324	0.1354	0.77793
90	0.2602	0.282	0.4578	0.34556	0.22766	0.03638	0.3026	0.84387
120	0.0303	0.2178	0.7519	0.48932	0.20034	0.15282	0.47701	0.87993
160	0	0.0119	0.9881	0.66399	0.14196	0.37032	0.67276	0.91269
210	0	1e-04	0.9999	0.80101	0.09715	0.57776	0.81558	0.95098
270	0	0	1	0.88234	0.06829	0.72003	0.89404	0.98476

Note: Bold doses indicate not meeting the overdose control criterion (more than 25% chance of over-dosing) with the prior information only.

Abbreviation: DLT = dose-limiting toxicity.

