20.1.1.3. Dose Recommended by the BLRM Method

The dose allocation will start at the dose of 20 mg. Patients will be included by cohort of 1 to 6 patients. There must be at least 3 DLT evaluable patients at a specific dose level if there is a DLT observed in that level. After each cohort of patients is completed, the dose recommendation by the model will be based on posterior summaries including the mean, median, standard deviation, 95% credible interval, and the probability that the true DLT rate for each dose lies in one of the following categories:

- (0, 16%]: under-dosing
- (16%, 33%]: targeted toxicity
- (33%, 100%]: over-dosing

Following the principle of EWOC, after each cohort of patients the recommended dose by the model is the one with the highest posterior probability of the DLT rate falling in the targeted toxicity interval (16%, 33%] among the admissible doses fulfilling EWOC, i.e., it is unlikely (< 25% posterior probability) that the DLT rate at the dose falls in the over-dosing interval.

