17.2.2 Final Recommendation and Stopping Rules

Dose escalation will continue until identification of the MTD(s) or suitable lower dose for recommended phase 2 dose(s) (the RP2D). This will occur when the following conditions are met:

1. At least 6 patients have been treated at this dose.
2. This dose satisfies one of the following conditions:
 - a. The posterior probability of targeted toxicity at this dose exceeds 50% and is the highest among potential doses, or
 - b. A minimum of 12 patients have already been treated on the trial.
3. It is the dose recommended for patients, by review of all clinical data by patients of the end of cohort meeting. Of note, the Dose Escalation part could be stopped earlier by a joint decision from the Sponsor and the Investigators during an SRC meeting, by considering the model estimations and a global assessment of the safety, PK, pharmacodynamics, and preliminary activity data.

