17.2.3.3 True Dose-DLT Scenarios

Simulations were performed on several true toxicity-dose relationships:

4. non-decreasing and finally reaching plateau
5. linear increasing (no plateau)
6. constant
7. increase steadily at the first beginning, and then increase much faster

Table13 True Underlying DLT Probabilities

Dose-limiting Toxicity (DLT) Scenarios	TP-0184 Dose Level (mg)							
	20	40	60	90	120	160	210	270
A	0.05	0.1	0.2	0.3	0.33	0.45	0.56	0.7
B	0.05	0.1	0.2	0.3	0.35	0.65	0.8	0.9
C	0.05	0.05	0.05	0.05	0.05	0.05	0.05	0.05
D	0.05	0.1	0.15	0.2	0.25	0.25	0.35	0.35

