17.2.3.4 Simulation Parameters

For each dose-DLT scenario, 5,000 clinical trial replications were generated using R software version 3.6.0 on a x86-64 architecture on a Windows OS. The Markov chain Monte Carlo (MCMC) estimation is obtained using R packages rjags and R2WinBUGS with 2,000 burn-in and 12,000 iterations on 2 chains (6,000 each). The seed used for MCMC estimation is 1 for chain 1 and 2 for chain 2.

Maximum number of patients of 30 was used. However, during the study, more patients may be added. The dose allocation rule used in the simulations is identical to the rule presented in [Section 20.1.1.3](#), ie, dose having the highest posterior probability of the DLT rate falling in the targeted interval (16%, 33%) among the admissible doses fulfilling EWOC.

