20.1.1.3.1. Evaluation Metrics

Operating characteristics were reviewed for the simulations to compare the relative performance of the design under each true dose-DLT relationship. The following metrics were:

- Probability of recommending as the MTD:
 - An under-toxicity dose level, i.e., a dose with true probability of DLT in the under-toxic interval (0%, 16%) (Sponsor risk)
 - A targeted-toxicity dose level, i.e., a dose with true probability of DLT in the targeted-toxicity interval (16%, 33%) (correct final decision)
 - An over-toxicity dose level, i.e., a dose with true probability of DLT in the over toxicity interval (33%, 100%) (patient risk)
- Average number of patients per trial exposed at:
 - An under-toxicity dose level, as defined above
 - A targeted-toxicity dose level, as defined above
 - An over-toxicity dose level, as defined above
- Summary of the total number of patients per trial (mean, first quartile, median, third quartile)
- Average total number of DLTs observed per trial

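### The BLRM prior labelled noninformative holds the model at 120 mg or below through about 30 DLT-free patients on the planned dose levels, and Table 14 cannot have come from the stated rule

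*Protocol*

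**What the plan says.** Protocol Appendix 2 sets out a two-parameter logistic model with reference dose 90 mg.

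- **Prior (Section 20.1.1.2, Table 11).** It is introduced by "The following noninformative prior for" log α and log β. The means are −0.847 and 0.913, the SDs 1.275 and 0.482, and the correlation −0.9. The SDs are said to be a choice "which allows for considerable prior uncertainty for the dose-toxicity profile".
- **Planned range (Section 20.1.1.1, Table 10).** "This study currently plans and expects to complete dose escalation with the following provisional dose levels": 20, 40, 60, 90, 120, 160, 210 and 270 mg, plus 10 mg as level −1. About 30 patients are planned in Phase 1.
- **Rule (Section 20.1.1.3).** The model picks the dose with the highest posterior probability of a DLT rate in (16%, 33%], among doses for which "it is unlikely (< 25% posterior probability) that the DLT rate at the dose falls in the over-dosing interval". Cohorts are of 1 to 6 patients, starting at 20 mg.
- **Stopping (Section 17.2.2).** At least 6 patients at the dose, plus either a target-interval probability above 50% that is the highest among the doses (2a), or "A minimum of 12 patients have already been treated on the trial" (2b). Clinical review is also required.
- **Simulations (Sections 17.2.3.3 and 17.2.3.4).** Four true DLT curves (Table 13), 5,000 trials each, at most 30 patients. "The dose allocation rule used in the simulations is identical to the rule presented in" Section 20.1.1.3. Results are in Table 14.
- **Closing text of 17.2.5.** No DLT in three patients generally leads to a higher dose.

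**The concern.** Table 12 is computed from the same prior. It gives probabilities of a DLT rate above 33% of 0.7519, 0.9881, 0.9999 and 1 at 120, 160, 210 and 270 mg. A prior that is almost certain that three of the eight planned levels are too toxic is not noninformative there. If about 30 clean patients cannot move it, the upper part of the plan is out of the model's reach however well the drug is tolerated, and the model-based MTD reflects the prior and not the observed DLTs.

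Table 14 should have shown this. Instead it shows 210 or 270 mg recommended in nearly a third of trials in scenario D, and exposure columns that fall far short of the number of patients treated. A reader relying on it would be misled about both correct selection and overdose risk.

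**Working it through.** **Inputs.** Table 11 prior, d* = 90 mg, Table 10 doses, the 25% limit of Section 20.1.1.3, Table 13 true rates, maximum 30 patients. Cohort size in the sponsor's simulations is not stated; sizes 1 to 6 were tried on DLT-free paths, and 3, 4 and 6 in the main simulation.

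**Formula.** logit π(d) = log α + β·log(d/90). P(over) at dose d is the posterior probability that π(d) > 0.33, obtained by grid integration of the bivariate normal prior times the binomial likelihood.

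**Step 1: reproduce the plan's figures.**

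| Dose (mg) | 20 | 40 | 60 | 90 | 120 | 160 | 210 | 270 |
|---|---|---|---|---|---|---|---|---|
| Table 12 P(over) | 0.057 | 0.140 | 0.245 | 0.458 | 0.752 | 0.988 | 0.9999 | 1 |
| Recomputed | 0.059 | 0.138 | 0.243 | 0.455 | 0.747 | 0.988 | 0.9999 | 1.0 |

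Table 15 scenario 7 also agrees: target 0.617 and over 0.120, against 0.6128 and 0.1222 printed. The model is being read as intended.

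**Step 2: DLT-free paths to 30 patients, planned levels, rule obeyed.** With cohorts of 1 to 6, with and without skipping levels, no path goes above 120 mg.

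- Most favourable type of path (for example 1, 1, 2, 8 and 18 patients at 20, 40, 60, 90 and 120 mg): P(over) at 160 mg is 0.729.
- Least favourable (5, 5, 5, 10, 5): 0.889.
- At 210 mg it is at least 0.995 on every path, and at 270 mg about 1.
- Bound independent of path: all 30 patients DLT-free at 120 mg, more than a compliant path can place there, gives 0.592 at 160 mg and 0.99 at 210 mg. About 85 DLT-free patients at 120 mg would be needed before 160 mg passes.
- Dosing 160 mg against the model would open it: after 0/3 at each of 20 to 120 mg plus 0/15 at 160 mg, P(over) there is about 0.22.
- With intermediate doses in 5 mg steps (the smallest capsule, Section 10.1), the model reaches 130 to 145 mg by 30 patients. P(over) at 160 mg is then 0.40 to 0.70; 160 mg becomes admissible at 35 to 48 DLT-free patients and 210 mg at 68 to 84.

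**Step 3: the 0/3 statement and Table 15.** After 0/3 at each of 20 to 90 mg, P(over) at 120 mg is 0.39, so the rule stays at 90 mg. After 0/3 at each of 20 to 120 mg, it is 0.94 at 160 mg, so the rule stays at 120 mg. Table 15 scenarios 5 to 9 therefore contain cohorts the rule would not have opened (0.35 to 0.39 at 120 mg, 0.93 to 0.94 at 160 mg). Scenario 2 prints 0.2312 at 90 mg, which is admissible; integration gives 0.260, which is not.

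**Step 4: Table 14 arithmetic, no simulation needed.** Section 20.1.1.3.1 describes the exposure columns as "Average number of patients per trial exposed at" under-toxic, targeted and over-toxic levels, so each row should sum to the mean trial size.

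| Scenario | Sum of exposure columns | Mean patients printed |
|---|---|---|
| A | 0.3 + 10.3 + 0 = 10.6 | 21.3 |
| B | 0.9 + 5.2 + 1.8 = 7.9 | 20.8 |
| C | 0.3 + 0 + 0 = 0.3 | 26.2 |
| D | 1.8 + 3 + 5.4 = 10.2 | 21.1 |

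Every trial starts at 20 mg, which is under-toxic in all four scenarios, so that column cannot be below 1; A, B and C print 0.3, 0.9 and 0.3. In C every dose has a true rate of 0.05, so 26.2 × 0.05 = 1.31 DLTs are expected; 0.1 is printed.

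**Step 5: recommendation probabilities.** The stated allocation rule was simulated with 5,000 trials per scenario, cohorts of 3, 4 and 6, and stopping as in Section 17.2.2, by 2a only, or none.

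| Quantity | Table 14 | Simulated |
|---|---|---|
| D: over-toxic dose (210 or 270 mg) recommended | 0.303 | 0; no patient at 160 mg or above |
| B: over-toxic dose recommended | 0.201 | at most 0.012 |
| A versus B: difference in under-toxic recommendation | 0.105 − 0.038 = 0.067 | at most 0.008 |
| C: no MTD | 0.985 | 0.02–0.04 as printed; 0.20–0.51 with 2a only |
| C: mean DLTs | 0.1 | 0.6–1.5 |

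A and B share true rates at 20 to 90 mg and differ at 120 mg only by 0.33 versus 0.35, so a large gap is not plausible. The Monte Carlo standard error of the printed gap is √(0.105×0.895/5000 + 0.038×0.962/5000) = 0.0051, so 0.067 is 13 standard errors. A separate simulation with 1,000 trials per setting, including random cohort sizes and two settings without overdose control, did not reproduce Table 14 either.

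**The case against.** - **The scenario letters may not line up.** The shapes listed in Section 17.2.3.3 do not follow the row order of Table 13. If Table 14 uses the listed order, its D could be Table 13 row B, whose over-toxic doses include 120 mg. The label inconsistency is real, but it does not rescue the table. Row B is the only row with an over-toxic dose the rule can reach, yet two rows of Table 14 print over-toxic recommendations (0.201 and 0.303). Under any relabelling, one of them needs 160 mg or above.
- **The simulated stopping rule is not stated.** Section 17.2.3.4 claims identity only for allocation, and clinical review cannot be simulated. This weakens scenario C's 0.985 as evidence, since the recomputed value depends on the stopping rule assumed; none of the variants comes near it. The exposure columns could count only trials that declared an MTD, but that would not explain the recommendation probabilities.
- **Table 15 is hypothetical.** It allows for medical review, and the 0/3 sentence is only a general statement. The next dose printed in scenarios 5 to 9 does follow from the data shown. Scenario 2 lies close to 25% and may be MCMC error. These are secondary points.
- **A cautious prior is the sponsor's choice, and Table 12 discloses it.** This is so, and the prior is worth only about 2 to 3 patients at 20 to 90 mg. The fault is the label together with a range the model cannot reach in the planned sample.
- **The model is guidance, levels are provisional, an MAD can be declared, and patients or intermediate doses can be added.** All true; the claim concerns the model's recommendation, not what the committee could decide.

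**Conclusion.** The concern holds. Under the Table 11 prior and the rule of Section 20.1.1.3, about 30 DLT-free patients on the planned levels leave the model at 120 mg, with overdose probability at 160 mg roughly three times the limit or more (0.73/0.25 = 2.9; 0.89/0.25 = 3.6). The bound with all 30 patients at 120 mg makes this independent of cohort size and path; permitted intermediate doses soften it but still leave 160 mg inadmissible at 30.

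Table 14 fails its own arithmetic as labelled, and its recommendation probabilities do not follow from the stated rule. The firmest items are the over-toxic recommendations and scenario C's DLT count; scenario C's no-MTD figure depends more on an unstated stopping rule.

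The error should be fixed, but its practical reach is limited. SAP Section 2 records termination after two patients, with listings only, so no reported result rests on these tables.

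**What to change.** Reconcile Table 11 with the planned range in Tables 3 and 10. The choice of prior and range is the sponsor's; two routes are open:

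1. Respecify a weakly informative prior. Check it on DLT-free paths and by simulation, including its behaviour at low doses and any skipping of levels.
2. Keep the prior, drop the word noninformative, and state the range the model can reach in about 30 patients.

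In either case:

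- re-run Tables 14 and 15 (and Table 12 if the prior changes) under Sections 20.1.1.3 and 17.2.2;
- state the cohort size and stopping rule used;
- align the scenario descriptions with Table 13 and define the exposure columns;
- use enough MCMC draws for decisions near 25% to be stable;
- correct the closing 0/3 statement in 17.2.5.

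The cost is computing time and a corrected appendix; no patients are needed. Route 1 has a price, which one illustration (not a recommendation) shows. Keeping the log α prior but giving log β mean 0, SD 1 and correlation 0 makes 120 and 160 mg admissible after 0/3 at every lower level (0.22 and 0.17). However, it raises prior P(over) at 20 mg from 0.059 to 0.133, makes 60 mg inadmissible before data (0.299), and after 0/3 at every level through 160 mg selects 270 mg (P(over) 0.196), skipping 210 mg. Route 2 avoids these costs but narrows the stated range.
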